6.2. KEY DEFINITIONS

For the purposes of this study, the term “study drug” refers to piromelatine or placebo.

The study day is the day relative to the date of first dose of study drug, where day -1 is the day before the first dose of study drug and day 1 is the day of first dose of study drug (Week 0 (Visit 2)).

The last dose date is defined as the last non-missing date where a nonzero dose of study drug was recorded.

Unless otherwise specified, baseline is the last non-missing observation before the start of the study treatment, which is expected to be the baseline visit at Week 0, or Screening (if existing) if the Week 0 data are not available.

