6.3. MISSING DATA

In cases of missing baseline data for cNTB tests, the pre-baseline value will be taken for analysis. If the pre-baseline value is missing as well, values from Screening will be taken and used for analysis as baseline. In cases where the baseline value for COWAT, CFT and ADAS-cog14 are missing, values obtained at Screening will be taken and used for analysis.

Pattern mixture model imputation will be used to treat missing data for all analyses of covariance (ANCOVA) as described in [Section 8.1](#). In the case of cNTB composite scores the imputation will be carried out at the level of the composite score, not at the level of individual tests.

Missing data for AEs where toxicity and relationship to study drug are missing will be treated as described in [Section 9.3](#).

Missing or partial dates for concomitant medications and adverse events will be treated as described in Sections [7.6](#) and [9.3](#) respectively.

No other imputation of missing data shall be performed.

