cNTB global composite scores and changes from baseline will be summarized (by treatment) at Visits 2, 3, 4 and 5. Change in cNTB global composite scores from baseline over 26 weeks (Visit 5) will be analyzed using a MMRM model utilizing all baseline and postbaseline data to assess any differences in treatment effects over time. The model will include fixed effects of treatment, study site, visit, and treatment by visit interaction, with baseline score, age, gender and ApoE4 as covariates, and a baseline by visit interaction. The global treatment effect estimates will be reported, with 95% confidence intervals and P values. Baseline will be the last non-missing observation at Visit 2 or before. The standard error of the change from baseline will also be included. The adjusted mean difference between treatments versus placebo will be presented along with the standard error and a 95% confidence interval.

These analyses will be performed by using PROC MIXED in SAS, and adjusted means will be obtained by using the LSMEANS statement.

An effect size calculation will be performed, where Cohen's d effect size will be calculated on the adjusted mean difference of change from baseline of treatment versus placebo. The effect size will be derived as the adjusted mean difference divided by the pooled standard deviation. The pooled within group variance (standard deviation squared) of two treatments is defined as:

$$\text{Pooled Variance} = [(n1 - 1)*\text{Var1} + (n2 - 1)*\text{Var2}] / (n1 + n2 - 2)$$

Where:

n1 = number of subjects with non-missing data for Placebo at Week 26

Var1 = variance for Placebo

n2 = number of subjects with non-missing data for active treatment at Week 26

Var2 = variance for active treatment

These analyses will be performed on the full analysis set and additionally on the per protocol set as a supportive analysis.

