A supportive efficacy analysis will be carried out using an ANCOVA method where the change in cNTB global composite scores from baseline to Week 26 will be the outcome variable and treatment group and study site will be main effects. cNTB global composite scores at baseline, age, gender, and ApoE4 will be included as covariates. The standard error of the change from baseline will also be included. Missing data (at the level of the composite score, not at the level of the individual tests) will be imputed using a pattern mixture model approach. Four patterns of missing data will be considered and imputed independently as follows:

- Pattern 1: will include patients who completed treatment on study drug (any missing data here is considered missing at random);
- Pattern 2: will include patients who discontinue treatment early due to adverse events (AEs);
- Pattern 3: will include patients who discontinue treatment early due to lack of therapeutic efficacy (LOTE);
- Pattern 4: will include patients who discontinue treatment early due to reasons other than AE event or LOTE.

The pattern mixture model methodology will be implemented using SAS procedures MI and MIANALYZE. Specifically, the following steps will be followed:

- Intermittent missing data will first be imputed using the Markov Chain Monte Carlo (MCMC) method implemented with the SAS MI procedure, which is appropriate for non-monotonic missing data.
- Data for patients who discontinue early will be multiply imputed as follows:
 - If the patient discontinues due to an AE (Pattern 2) or LOTE (Pattern 3), then missing data will be assumed to follow a distribution similar to the baseline values observed in the placebo arm of the study;
 - If the patient discontinues due to reasons other than an AE or LOTE (Pattern 4), at each time point, missing data will be assumed to follow a distribution similar to scores for patients that are still in the study and randomized to the same treatment group.
- Results of the ANCOVA on the multiply imputed data will be summarized using the SAS procedure MIANALYZE.

These analyses will be performed on the full analysis set and additionally on the per protocol set as a supportive analysis.

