8.2.3. Alzheimer's Disease Assessment Scale Cognitive 14 Subscale

The ADAS-cog consists of 11 tasks measuring the disturbances of memory, language, praxis, attention, and other cognitive abilities that are often referred to as the core symptoms of AD. The test comprises 11 items summed to a total score ranging from 0 to 70, with lower scores indicating less severe impairment. A negative change indicates an improvement from baseline. The addition of delayed recall, number cancellation, and maze tasks - and thus turning ADAS-cog into a 12-, 13-, and 14-item scale, respectively - has increased the ability to detect changes in patients in the early stages of the disease.

The ADAS-cog14 global scores and changes from baseline will be summarized (by treatment) at each visit. Change in ADAS-cog14 scores from baseline over Week 26 (Visit 5) will be analyzed using a MMRM model utilizing all baseline and postbaseline data to assess any differences in treatment effects over time. The model will include fixed effects of treatment, study site, visit, and treatment by visit interaction, with baseline score, age, gender and ApoE4 as covariates, and a baseline by visit interaction. The global treatment effect estimates will be reported, with 95% confidence intervals and *P* values. Baseline will be the last non-missing observation at Visit 2 or before. The adjusted mean difference between treatments versus placebo will be presented along with the standard error and a 95% confidence interval.

These analyses will be performed using PROC MIXED in SAS, and adjusted means will be obtained by using the LSMEANS statement.

An effect size calculation will be performed, where Cohen's *d* effect size will be calculated on the adjusted mean difference of change from baseline of treatment versus placebo. The effect size will be derived as the adjusted mean difference divided by the pooled standard deviation.

A supportive analysis will be carried out using an ANCOVA method where the change in ADAS-cog14 scores from baseline to Week 13 (Visit 4) and Week 26 (Visit 5) will be the outcome variable and treatment group and study site will be main effects. The ADAS-cog14 scores at baseline, age, gender and ApoE4 will be included as covariates. Baseline will be the last non-missing observation at Visit 2 or before. Multiple imputations for

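### The cNTB and ADAS-cog14 models adjust only for the last pre-treatment score; adding the earlier scores that section 6.3 implies would be a cheap precision gain of uncertain, possibly small, size

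*SAP*

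**What the plan says.** The primary MMRM in section 8.1 has treatment, site, visit and treatment by visit as fixed effects, "with baseline score, age, gender and ApoE4 as covariates, and a baseline by visit interaction". The supportive ANCOVA in the same section follows suit: "cNTB global composite scores at baseline, age, gender, and ApoE4 will be included as covariates". Section 6.2 makes baseline one value: "baseline is the last non-missing observation before the start of the study treatment". Sections 8.1 and 8.2.3 repeat this in the form "Baseline will be the last non-missing observation at Visit 2 or before".

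Section 6.3 shows that earlier values are expected. For the cNTB tests: "In cases of missing baseline data for cNTB tests, the pre-baseline value will be taken for analysis", and then "If the pre-baseline value is missing as well, values from Screening will be taken and used for analysis as baseline". For the two paper tests and ADAS-cog14: "In cases where the baseline value for COWAT, CFT and ADAS-cog14 are missing, values obtained at Screening will be taken and used for analysis". No other section gives these values a role in the models. Section 8.1 does describe the MMRM as using all baseline and post-baseline data, but the terms it lists contain one baseline score only.

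**The concern.** One testing session measures a patient's underlying level with error. A second or third pre-treatment score usually carries further information on the Week 26 score, and a model that leaves it out has a larger residual variance than it needs.

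Precision is a live issue here. Section 10 reports that planned power was lowered from 88% to 80%, and it combines the 20 mg and 50 mg arms in an exploratory analysis to gain power. Combining arms changes the question asked. An extra pre-treatment covariate leaves each dose-versus-placebo question as it is. Because the values precede double-blind treatment, practice effects common to the arms do not bias the contrast.

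**Working it through.** **Inputs from the SAP (section 3.6).** Effect size d = 0.35, one-sided alpha 0.05, 115 placebo and 95 per active arm, stated power 80%.

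**Inputs not in the SAP, so assumed.** The correlation r of each pre-treatment score with the Week 26 score; the correlation c between pre-treatment scores; and that 0.35 is on the residual scale of the planned one-baseline model. The calculation treats Week 26 as a single time point.

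**1. Reproduce the plan.** Noncentrality = 0.35 × √(115 × 95 / 210) = 2.52. The noncentral t distribution with 208 degrees of freedom gives power 80.8%, in line with the stated 80%. A two-sided 0.05 test would give about 71%, so the plan's figure is the one-sided one.

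**2. Formula.** With k pre-treatment scores as covariates, R² = k r² / (1 + (k − 1) c). With one score, R² = r². The residual variance ratio is f = (1 − R²) / (1 − r²). The standard error is multiplied by √f, and power is recomputed with 0.35/√f.

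**3. Equal correlation (c = r), the favourable case.**

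| r = c | k | f | Power | Gain (points) |
|---|---|---|---|---|
| 0.5 | 2 | 0.889 | 84.7% | 3.9 |
| 0.5 | 3 | 0.833 | 86.7% | 5.9 |
| 0.7 | 2 | 0.830 | 86.8% | 6.0 |
| 0.7 | 3 | 0.760 | 89.3% | 8.5 |

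For example, with r = 0.7 and k = 3: R² = 3 × 0.49 / 2.4 = 0.6125, and f = 0.3875 / 0.51 = 0.760.

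**4. Pre-treatment scores closer to each other than to Week 26 (c > r).**

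| r | c | k | f | Power | Gain (points) |
|---|---|---|---|---|---|
| 0.50 | 0.80 | 3 | 0.949 | 82.6% | 1.8 |
| 0.60 | 0.80 | 3 | 0.913 | 83.8% | 3.0 |
| 0.70 | 0.85 | 2 | 0.922 | 83.5% | 2.7 |
| 0.70 | 0.85 | 3 | 0.893 | 84.6% | 3.7 |
| 0.70 | 0.80 | 3 | 0.852 | 86.0% | 5.2 |

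If Screening predicts Week 26 less well than baseline does (0.65 v 0.70, with 0.80 between them, two scores), f = 0.956, power is 82.4% and the gain is 1.5 points.

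**5. Correlation decaying with time.** Assume sessions at weeks −4, −2 and 0, a true-score correlation of 0.70 or 0.85 over 26 weeks, and reliability 0.7 to 0.9. Three scores then cut the residual variance by 3.2% to 12.7%. Power is 81.9% to 85.3%, a gain of 1.1 to 4.5 points. With reliability 1.0 (an error-free Markov score) the gain is zero.

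**6. If 0.35 is on the raw Week 26 SD instead.** The planned model then works with 0.35/√(1 − r²), so power is already 89.6% at r = 0.5 and 97.0% at r = 0.7. Even under equal correlation, three scores add only 4.2 and 2.2 points.

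**The case against.** The strongest reply is that nothing here is wrong. A last-non-missing baseline covariate is conventional, clearly specified and unbiased. A reader might infer from section 6.3 that the primary analysis is defective, or that every cNTB and ADAS-cog14 comparison necessarily has an inflated standard error. The documents support neither: the gain is zero in a limiting case, and the SAP gives no correlation from which to establish its size. Nor do the cut to 80% power and the pooled arms show an error. Section 10 calls 80% acceptable, and the pooled comparison is exploratory.

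A reader might also take gains of 6 to 9 points as the expected benefit. Those need pre-treatment scores to correlate no better with each other than with a score 26 weeks later. In a progressive disease, sessions close together would be expected to correlate more strongly, which points to the 1 to 5 point range.

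Two further objections stand. Section 6.3 is a missing-data rule: it does not date the pre-baseline value or show how completely it is collected. Section 6.2 qualifies Screening data as existing only in some cases, and section 3.9 leaves the schedule to the protocol. Also, the power figures treat the scores as exchangeable full composites. For COWAT and CFT only Screening is named as a fallback ("In cases where the baseline value for COWAT, CFT and ADAS-cog14 are missing, values obtained at Screening will be taken"), so a pre-baseline composite may hold only the six computerised tests. Those six can still meet the section 8.1 minimum of five tests with at least one per domain, but the gain from such a mixed covariate may differ from the tables.

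What does not stand is that this is mere taste. The change is specific, keeps the treatment question, cannot bias the contrast and costs little.

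**Conclusion.** The point holds as a low-cost improvement to a valid analysis. The models in sections 8.1 and 8.2.3 adjust for one pre-treatment score while section 6.3 points to earlier ones kept as fallbacks, so some precision is probably lost.

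With 0.35 on the residual scale, a gain of about 1 to 5 points over 80.8% is the more plausible range; about 4 to 9 points requires equal correlation of 0.5 to 0.7; near zero is possible. If 0.35 is on the raw scale, which section 3.6 does not settle, the gain is generally smaller. All of this also depends on the earlier values being routinely collected, which the SAP alone does not establish.

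**What to change.** First confirm in the assessment schedule which earlier values are routinely collected. If only Screening is complete, use that alone. Then, before unblinding:

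- **Section 8.1.** Keep the change score and the Visit 2 baseline. Add one prespecified covariate: the mean of the available earlier pre-treatment composites that meet the section 8.1 minimum-test rule, z-scored with the study-baseline mean and SD. In the MMRM include its interaction with visit; in the ANCOVA enter it as a main effect.
- **Missing or already used values.** Where no earlier value exists, or where the earlier value already serves as baseline under section 6.3, set the covariate equal to the baseline score, so that no patient is dropped.
- **Section 8.2.3.** Do the same with the Screening ADAS-cog14 value.

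The cost is a few sentences, one derived variable and a few degrees of freedom, with no new data. The gain is uncertain and may be small.

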8.2. SECONDARY EFFICACY ENDPOINTS AND ANALYSES

8.2.1. Clinical Global Impression of Change

The CGIC is a single score with ordered values of 1 to 7 for “marked improvement” to “marked worsening”. A negative change from baseline indicates an improvement.

Since the result for CGIC is one of a set of ordered scores, the number and percentage of patients with each score at each visit (Week 13 and Week 26) will be provided. The difference between groups will be evaluated by means of the van Elteren version of the Cochran-Mantel-Haenszel test and *P* values will be presented.

8.2.2. Alzheimer’s Disease Cooperative Study/Activities of Daily Living Scale Adapted for MCI Patients

The Alzheimer’s Disease Cooperative Study/Activities of Daily Living Inventory (ADCS-ADL) score is the total of scores from 18 (questions 19-24 shall not be analyzed for this endpoint) multiple-choice questions. Higher total scores mean better performance; a positive change from baseline indicates an improvement. Many of the questions begin with a selection of yes, no or don’t know, with no or don’t know given scores of 0 and yes leading to the multiple choices. Scores including many don’t know responses could be less reliable than scores with fewer such responses.

The ADCS-ADL global scores and changes from baseline will be summarized (by treatment) at each visit. Change in ADCS-ADL scores from baseline to Week 26 (Visit 5) will be analyzed using a MMRM model utilizing all baseline and postbaseline data to assess any differences in treatment effects over time. The model will include fixed effects of treatment, study site, visit, and treatment by visit interaction, with baseline score, age, gender and ApoE4 as covariates, and a baseline by visit interaction. The global treatment effect estimates will be reported, with 95% confidence intervals and *P* values. Baseline will be the last non-missing observation at Visit 2. The standard error of the change from baseline will also be included. The adjusted mean difference between treatments versus placebo will be presented along with the standard error and a 95% confidence interval.

These analyses will be performed using PROC MIXED in SAS, and adjusted means will be obtained by using the LSMEANS statement.

An effect size calculation will be performed, where Cohen’s *d* effect size will be calculated on the adjusted mean difference of change from baseline of treatment versus placebo. The effect size will be derived as the adjusted mean difference divided by the pooled standard deviation.

These analyses will be performed on the full analysis set and additionally on the per protocol set as a supportive analysis.

A supportive efficacy analysis will be carried out using an ANCOVA method where the change in ADCS-ADL scores from baseline to Week 13 (Visit 4) and Week 26 (Visit 5) will be the outcome variable and treatment group and study site will be main effects. The ADCS-ADL scores at baseline, age, gender and ApoE4 will be included as covariates. Multiple imputation for missing values will take place using the pattern mixture model approach, as described in [Section 8.1](#). The standard error of the change from baseline will also be included. The adjusted mean difference between treatments versus placebo will be presented along with the standard error and a 95% confidence interval.

These analyses will be performed on the full analysis set and additionally on the per protocol set as a supportive analysis.

8.2.3. Alzheimer's Disease Assessment Scale Cognitive 14 Subscale

The ADAS-cog consists of 11 tasks measuring the disturbances of memory, language, praxis, attention, and other cognitive abilities that are often referred to as the core symptoms of AD. The test comprises 11 items summed to a total score ranging from 0 to 70, with lower scores indicating less severe impairment. A negative change indicates an improvement from baseline. The addition of delayed recall, number cancellation, and maze tasks - and thus turning ADAS-cog into a 12-, 13-, and 14-item scale, respectively - has increased the ability to detect changes in patients in the early stages of the disease.

The ADAS-cog14 global scores and changes from baseline will be summarized (by treatment) at each visit. Change in ADAS-cog14 scores from baseline over Week 26 (Visit 5) will be analyzed using a MMRM model utilizing all baseline and postbaseline data to assess any differences in treatment effects over time. The model will include fixed effects of treatment, study site, visit, and treatment by visit interaction, with baseline score, age, gender and ApoE4 as covariates, and a baseline by visit interaction. The global treatment effect estimates will be reported, with 95% confidence intervals and *P* values. Baseline will be the last non-missing observation at Visit 2 or before. The adjusted mean difference between treatments versus placebo will be presented along with the standard error and a 95% confidence interval.

These analyses will be performed using PROC MIXED in SAS, and adjusted means will be obtained by using the LSMEANS statement.

An effect size calculation will be performed, where Cohen's *d* effect size will be calculated on the adjusted mean difference of change from baseline of treatment versus placebo. The effect size will be derived as the adjusted mean difference divided by the pooled standard deviation.

A supportive analysis will be carried out using an ANCOVA method where the change in ADAS-cog14 scores from baseline to Week 13 (Visit 4) and Week 26 (Visit 5) will be the outcome variable and treatment group and study site will be main effects. The ADAS-cog14 scores at baseline, age, gender and ApoE4 will be included as covariates. Baseline will be the last non-missing observation at Visit 2 or before. Multiple imputations for

missing values will take place using the pattern mixture model approach, as described in [Section 8.1](#). The standard error of the change from baseline will also be included. The adjusted mean difference between treatments versus placebo will be presented along with the standard error and a 95% confidence interval.

These analyses will be performed on the full analysis set and additionally on the per protocol set as a supportive analysis.

8.2.4. Computerized Neuropsychological Test Battery Global Composite Score

Change in cNTB global composite scores from baseline to Week 4 (Visit 3) and from baseline to Week 13 (Visit 4) will be analyzed using a MMRM model utilizing all baseline and postbaseline data to assess any differences in treatment effects over time. The model will include fixed effects of treatment, study site, visit, and treatment by visit interaction, with baseline score, age, gender and ApoE4 as covariates, and a baseline by visit interaction. The global treatment effect estimates will be reported, with 95% confidence intervals and *P* values. Baseline will be the last non-missing observation at Visit 2 or before. The standard error of the change from baseline will also be included. The adjusted mean difference between treatments versus placebo will be presented along with the standard error and a 95% confidence interval.

These analyses will be performed using PROC MIXED in SAS, and adjusted means will be obtained by using the LSMEANS statement.

An effect size calculation will be performed, where Cohen's *d* effect size will be calculated on the adjusted mean difference of change from baseline of treatment versus placebo. The effect size will be derived as the adjusted mean difference divided by the pooled standard deviation.

These analyses will be performed on the full analysis set and additionally on the per protocol set as a supportive analysis. A supportive efficacy analysis will be carried out using an ANCOVA method where the change in cNTB global composite scores from baseline to Week 4 (Visit 3) and Week 13 (Visit 4) will be the outcome variable and treatment group and study site will be main effects. cNTB global composite scores at baseline, age, gender and ApoE4 will be included as covariates. The standard error of the change from baseline will also be included. Multiple imputation for missing values (at the level of the composite score, not at the level of the individual tests) will take place using the pattern mixture model approach, as described in [Section 8.1](#). The adjusted mean difference between treatments versus placebo will be presented along with the standard error and a 95% confidence interval. Global composite scores will be calculated as described in [Section 8.1](#).

These analyses will be performed on the full analysis set and additionally on the per protocol set as a supportive analysis.

